16.0 Potential Benefits to Subjects

16.1 Describe the potential benefits that individual subjects may experience from taking part in the research. Include as may be useful for the IRB's consideration, the probability, magnitude, and duration of the potential benefits.

Potential benefits to subjects may include increase in PA, as well as a decrease in ADHD symptoms and associated behavioral difficulties through participation in the BMT program.

17.0 Vulnerable Populations

The research is minimal risk as child participants will not be engaging in any activity that carries significantly greater risk than what they would likely already be doing as a child. Wearing the activity tracker does introduce monitoring of activity so it is possible that they may feel encouraged to be more active.

Children's caregivers may provide additional opportunities for physical activity but these would unlikely significantly increase their level of risk.. Adult participants will not be prescribed any intense physical activity as part of the study. The activity meter is worn on a soft elastic belt and has been used in several other studies within our research group and department without incident. We have used similar versions of the Garmin Vivofit activity tracker in previous research studies with no issues or complaints.

18.0 Community-Based Participatory Research

N/A

19.0 Sharing of Results with Subjects

Data analysis, manuscript writing, publications, and presentations will all be derived from de-identified data; all research products (e.g. publications, presentations) will be double checked for possible identifying information prior to submission. Results and research products will be shared with participants once finalized post analyses and publication.

20.0 Setting

20.1 Describe the sites or locations where your research team will conduct the research.

Potential subjects will be identified and recruited through primary care and specialty clinics affiliated with Seattle Children's Hospital. Screening visits and BMT program meetings will take place at the Seattle Children's main campus in Seattle, WA.

21.0 Resources Available

21.1 Describe the qualifications (e.g., training, education, experience, oversight) of you and your staff as required to perform their role. When applicable describe their knowledge of the local study sites, culture, and society. Provide enough information to convince the IRB that you have qualified staff for the proposed research.

The PIs of the study include a clinical psychologist with expertise in psychosocial treatments and health risk behaviors associated with ADHD ([name]) and a general pediatrician and PA researcher with a k23 Career Development Award focused on promoting PA and outdoor time in early childhood ([name]).

The CRA for the study has extended experience working with accelerometry data and Garmin wearable technology.

21.2 Describe other resources available to conduct the research: For example, as appropriate:

- Justify the feasibility of recruiting the required number of suitable subjects within the agreed recruitment period. For example, how many potential subjects do you have access to? What percentage of those potential subjects do you need to recruit?*

We will recruit participants through primary care and specialty clinics affiliated with Seattle Children's Hospital. This strategy was effective in several prior studies conducted by the study team. Within the PEARL Clinic, an ADHD specialty clinic within outpatient psychiatry, 484 unique patients were seen in 2016, of which 210 were ages 6-8 years. Medical and mental health providers will be asked to disseminate study information to ADHD-diagnosed youth under their care in the PEARL Clinic and outpatient psychiatry. Since the majority of youth with ADHD are treated in primary care, we will also distribute study information to local primary care clinics. Co-PI [name] is a provider in the Roosevelt Clinic through UW, where she can coordinate recruitment efforts. Advertisements via Facebook, one of the platforms to be used in the intervention, and through the Seattle Children's Hospital and Seattle Children's Research Institute website will be used if needed. These methods have worked well in prior studies by the co-PIs and Co-Is. If such advertisements are needed, we will submit the proposed ad to the IRB for approval.

Describe the time that you will devote to conducting and completing the research.

The grant provides for protected time for the PIs and Co-Is to conduct the proposed research.

- *Describe your facilities.*
Assessments and study groups will be conducted at Seattle Children's Hospital. The co-PI ([name]) and several of the Co-Is ([name], [name]) have offices there. There are private treatment and group rooms available for the study.
- *Describe the availability of medical or psychological resources that subjects might need as a result of an anticipated consequences of the human research.*

Physical activity is taking place in the participants' own homes and neighborhoods. We will refer patients to consult regarding fitness-related concerns or injuries with their primary care doctor. The need for additional psychological resources will be assessed by the Co-PIs or Co-Is. Emergency services are available at Seattle Children's. We will facilitate referrals for individual mental health treatment within Outpatient Psychiatry or in the community if needed.

- *Describe your process to ensure that all persons assisting with the research are adequately informed about the protocol, the research procedures, and their duties and functions.*

Upon hiring, the co-PIs will provide training in the study protocol to all hired research assistants or other personnel working on the study. Job descriptions will be provided prior to hiring. The co-PIs will supervise all personnel on the study.

22.0 Prior Approvals

N/A

23.0 Recruitment Methods

23.1 *Describe when, where, and how potential subjects will be recruited.*

Subjects will be recruited through a Seattle Children's Hospital-based specialty ADHD Clinic and primary care clinics associated with Seattle Children's (Roosevelt clinic; Harborview Primary Care). One of the Co-PIs ([name]) is a provider in the Program to Enhance Attention Regulation and Learning (PEARL) Clinic in Outpatient Psychiatry at SCH, the other Co-PI ([name]) is a provider at the Roosevelt Clinic, and one of the Co-Is ([name]) is a provider at Harborview Primary Care. Within the PEARL Clinic, 484 unique patients were seen in 2016, of which 210 were ages 6-8. Medical and mental health providers will be asked to disseminate

study information via a study flyer to ADHD-diagnosed youth under their care in PEARL and outpatient psychiatry. We will send letters to families on the PEARL Clinic wait list and former PEARL Clinic patients. We will also have a study description in the PCP referral system to the PEARL Clinic, so PCPs will see a description of the LEAP study in the list of studies that get faxed back to PCPs when the PEARL Clinic not accepting new referrals. Because the majority of youth with ADHD are treated in primary care⁸⁵, we will also distribute study information to the Roosevelt associated with Seattle Children's to be posted in waiting areas and given to providers to distribute to patients with ADHD. Recruitment will take place during the first phase of the project and will be rolling until all treatment groups have been filled.

23.2 Describe the source of subjects.

Please see above for information regarding the PEARL clinic and primary care clinics, as well as Facebook/Instagram advertisements.

23.2 Describe the methods that will be used to identify potential subjects.

Providers will be asked to distribute study flyers to patient with ADHD diagnosis or probable ADHD. Flyers will direct interested families to a website customized for the present study, which will connect them with study staff for further information. The website will contain only study title, purpose of study, protocol summary, basic eligibility criteria, study site locations, how to contact the study site for more info. The Facebook/Instagram ad (to be submitted via Modification) will be run three times weekly during the recruitment period, directed at users who are caregivers of school-aged children. The link will direct interested individuals to a study website with contact information for the study coordinator.

23.3 Describe materials that will be used to recruit subjects. (Attach copies of these documents with the application. For printed advertisements, attach the final copy. For online advertisements, attach the final screen shots (including any images). When advertisements are taped for broadcast, attach the final audio/video tape. You may submit the wording of the advertisement prior to taping to preclude re-taping because of inappropriate wording, provided the IRB reviews the final audio/video tape.)

Facebook/Instagram advertisement will be submitted via modification. If the participant consents to participate in the study then information collected during the pre-screening phone call will be kept in a locked cabinet. If the participant does not wish to participate or does not sign a consent form then the information collected during the pre-screening interview will be destroyed.

23.4 Describe the amount, method (e.g. gifts, check, gift cards) and timing of any payments to subjects. Provide details on who will be the recipient of the payment (caregiver or child).

For each assessment visit (screening visit, Baseline, 5 week and 9 week assessments), subjects will receive parking validation. Participants will receive compensation for completing study assessments in the following amounts: (1) \$15 for screening visit and completion of accelerometry screening; (2) \$25 for baseline battery completion (3) \$25 for Week 5 (4) \$50 for week 9 (5) \$15 for participating in focus group. Supplementary caregivers will not receive any payment for participating. The amount will total \$130 per family. Up to \$20 will be provided for each group session for families that need to purchase childcare, totaling up to \$160 per family for childcare reimbursement. Teachers will be reimbursed \$10 for each of the two questionnaire batteries they are asked to complete (baseline and 9 weeks).

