3.4 Screening Visit

Screening visits will be completed within 60 days of group treatment start. Eligible participants will be enrolled on the same day as the screening visit.

Diagnostic evaluation will consist of structured interviewing with the child and caregiver on the *Schedule for Affective Disorders for School-Aged Children (K-SADS) Present and Lifetime Version (K-SADS-PL)*,[35] which assesses current and past presence of DSM-5 disorders in ages 6-18. Interviewing will be completed by a licensed psychologist or supervised pre- or post-doctoral trainee. The K-SADS-PL has strong test-retest and inter-examiner reliability, with kappas for ADHD above .70.[36] Inter-examiner reliability will be established and monitored over the trial by taping interviews and randomly selecting 20% for reliability checks. Should kappas fall < .70, additional training will be provided.

The Clinical Global Impressions (CGI-S) ADHD Severity Scale,^[37] a clinician-rated, 7-point scale that describes the severity of ADHD symptoms (using the K-SADS), will be used to screen for ADHD severity. Children must have a current CGI-S rating >4 to participate. The CGI-S also serves as an exploratory outcome in the R21 phase and a secondary outcome in the R33 phase.

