7.0 Study Timelines

7.1 *Describe:*

- *The duration of an individual subject's participation in the study.*
For participants in the BMT-Health group intervention – approx. 9 - 16 weeks from the date of screening/baseline enrollment
- *The duration anticipated to enroll all study subjects.*
Using a rolling recruitment approach, enrollment for the entire study is anticipated to take 2 years.
- *The estimated date for the investigators to complete this study (complete primary analyses)*
The estimated date for completion of this study is January 2020.

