Feasibility	Garmin (wear time), Facebook likes and comments	G/P/C	E, SE			X	X
Acceptability	Attendance, TAI	P	CR, DP			X	X
Acceptability	CSQ, Focus group		DP				X
Executive function	SSRT, DS, BRIEF-2	C/P	SE		X		X
ADHD symptoms	Conners-3 (P), Vanderbilt (T)	P/T	DP		X		X
Functional impairment	IRS	P/T	DP		X		X
Parenting	APQ	P	DP		X		X
PA, Sleep, Media use	HBS	P	DP		X	X	X
Sleep problems	CSHQ	P	DP		X		X
BMI	Height, weight	C	SE		X		X
Complementary/Alternative medicine use	HBS	P	DP		X		X
Media Use	Problematic Media Use	P	DP		X		X
Medication use	HBS	P	DP		X	X	X
Mindfulness	Mindful Attention Awareness		DP		X	X	X

	Scale							
Socio-demographics	Survey	P	DP			X		

APQ = *Alabama Parenting Questionnaire*. BMI = *Body Mass Index*. BRIEF = *Behavior Rating Inventory of Executive Function*. CGI-S = *Clinician Global Impressions Scale – Severity*. Conners-3 = *Conners-Third Edition*. CSHQ = *Children's Sleep Habit Questionnaire*. CSQ = *Client Satisfaction Questionnaire*. DS = *Digit Span task*. ERC = *Emotion Regulation Checklist*. FW = *Finger Windows task*. HBS = *Health Behaviors Survey*. IRS = *Impairment Rating Scale*. K-SADS-PL = *Kidnie-SADS-Present and Lifetime Version*. MVPA = *Moderate-to-Vigorous Physical Activity*; PA = *Physical Activity*. SSRT = *Stop-Signal Reaction Time task*. TAI = *Treatment Adherence Inventory*. A = *Actigraph GT3x+*; C = *Child*; G = *Garmin Device*; P = *Parent*; T = *Teacher*. DP=digitally entered by parent/caregiver; CR=Clinician rated; E=electronic device data; SE =study staff entered

For the K-SADS instrument:

- the Pregnancy and Birth Questions will not be included
- the Family History for Biological Relatives will not be included

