11.0 Data Analysis/Management

Describe the data analysis plan, including any statistical procedures.

Given the pilot nature of the R21 study, data analysis will be largely descriptive and exploratory. We will focus on parameter estimates instead of formal hypothesis testing. The feasibility and acceptability of the research protocol as outlined above is the main outcome of interest, as is now recommended for pilot studies, rather than effect size estimates.¹⁰⁹

Study aim 1: To test the feasibility and acceptability of the intervention

Feasibility will be assessed by (a) demand through inquiry and enrollment rates and (b) practicality and participation through attrition rates and adherence with intervention (attendance, percentage of days wearing and syncing Garmin, participation in Facebook group) and study procedures (screening, follow-up batteries, accelerometry).

Acceptability will be assessed through participant ratings and qualitative interviews.

Fidelity of the social media/text component will be evaluated following a procedure for prior mHealth intervention pilots conducted by the study team including tracking facilitator posts, participant views, likes, and posts. We will summarize the measures listed above using means, medians, and standard deviations for continuous variables and proportions for categorical variables and then conduct bivariate analyses. Non-parametric tests will be used on non-normally distributed continuous variables, and Fisher's exact test on sparse categorical variables. The proportions that reflect acceptability and feasibility will be assessed using 95% exact (Clopper-Pearson) confidence intervals

Exploratory Aim: To explore the effects of the intervention on PA

We will compare within-subject pre to post activity using accelerometer data (step count; sedentary, light and MVPA; sleep duration), MVPA as an exploratory outcome. We will examine gender as an effect modifier given that differences in PA are seen between boys and girls from an early age and differential effects of previous PA interventions by gender have been noted.(111) We will also look at associations of the measures from Aim 1 with PA outcomes. Pre- and post-intervention outcomes will be compared using t-

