tests, paired t-tests, chi-square and when appropriate, Fisher's exact test. We will account for within-subject correlation due to repeated measures. Due to the pilot nature of the intervention, we emphasize the analyses will be primarily descriptive; confirmatory analysis will await future studies.

11.1 Provide a power analysis.

We anticipate needing to screen up to 45 children for low PA to ensure enrollment of 30 eligible families, but will screen more if needed. Treatment groups will begin on a rolling basis as soon as 6-8 eligible families have enrolled.

11.2 Describe any procedures that will be used for quality control of collected data.

N/A

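### Rolling group starts ignore the school calendar, so some single-arm before-after comparisons will set a term-time measurement against one from a school break

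*Combined protocol and SAP*

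**What the plan says.** **Timing of starts.** Section 7.1: "Using a rolling recruitment approach, enrollment for the entire study is anticipated to take 2 years". Section 11.1: "Treatment groups will begin on a rolling basis as soon as 6-8 eligible families have enrolled". Section 3.4: "Screening visits will be completed within 60 days of group treatment start". Section 7.1 puts a family's participation at about "9 - 16 weeks from the date of screening/baseline enrollment".

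**Measurements.** Table 2 in Section 9.2 schedules seven-day accelerometry at baseline and 9 weeks. It schedules the teacher Vanderbilt and the Impairment Rating Scale (IRS, parent and teacher) at the same two points, with no teacher rating at 5 weeks. Section 23.4 confirms this: teachers are reimbursed for "each of the two questionnaire batteries they are asked to complete (baseline and 9 weeks").

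**Analysis.** Section 1.1 makes an estimate of the effect size on physical activity the second specific aim. Section 11.0 compares accelerometer data within child, before and after, and has no control group. A general sentence follows: "Pre- and post-intervention outcomes will be compared using t"-tests, paired t-tests, chi-square or Fisher's exact test. Section 11.0 also counts adherence with follow-up batteries and accelerometry among the feasibility measures.

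**What is absent.** Neither the school calendar nor a change of teacher appears in the documents. Nor do they say what happens when a teacher rating cannot be obtained.

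**The concern.** The children are 5-10 years old, so school weeks and break weeks are different settings for activity. The plan itself treats school as a source of activity: the clinic survey in Section 2.2 asks about days of physical education at school. With no comparison arm, nothing removes a setting difference between the two wears. It goes straight into the within-child change that serves the second aim.

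The teacher batteries raise a related problem. A battery due in the break may be missing, late, or completed by a teacher who no longer sees the child. Counted as non-completion, it reads as poor feasibility although the cause is the calendar. Analysed as it stands, it reads as change in the child. If the second rating comes from a new teacher, a difference between raters does the same.

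Teachers are the only raters outside both the family and the study team, which makes their ratings worth protecting.

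**Working it through.** The plan gives no figure for this, so there is nothing to reproduce. The check is one of timing.

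**Inputs from the documents**
- Follow-up is at 9 weeks, and screening may precede group start by up to 60 days. If baseline is done at screening, the interval *g* runs from 9 weeks to 9 + 60/7 = 17.6 weeks. Section 7.1 says about 9-16 weeks.
- The target is 30 families in groups of 6-8, so 30/8 = 3.75 to 30/6 = 5, that is about 4-5 groups.

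**Assumptions, not in the documents**
- The summer break *b* lasts 8, 10 or 12 weeks.
- Baseline dates are spread evenly over a 52-week year.
- Shorter breaks are ignored.

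**Formulas**
- Exactly one of two measurements in the break: 2·min(g, b)/52
- At least one in the break: [2b − max(b − g, 0)]/52
- Both in term, on opposite sides of the summer: max(g − b, 0)/52
- Any overlap of the interval with the break: (g + b)/52

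| b | g | exactly one in break | at least one in break | both in term, opposite sides | any overlap |
|---|---|---|---|---|---|
| 8 | 9 | 31% | 31% | 2% | 33% |
| 8 | 16 | 31% | 31% | 15% | 46% |
| 8 | 17.6 | 31% | 31% | 18% | 49% |
| 10 | 9 | 35% | 37% | 0% | 37% |
| 10 | 16 | 38% | 38% | 12% | 50% |
| 10 | 17.6 | 38% | 38% | 15% | 53% |
| 12 | 9 | 35% | 40% | 0% | 40% |
| 12 | 16 | 46% | 46% | 8% | 54% |
| 12 | 17.6 | 46% | 46% | 11% | 57% |

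**Activity.** Of 30 children, 0.31 × 30 to 0.46 × 30, about 9-14, would have one wear in the break and one outside it. Half of these shifts go each way on average, so they cancel in expectation. With 4-5 groups, start dates are clustered and opposite shifts need not balance in the trial that is run.

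**Teacher batteries.** In 31-46% of children at least one battery falls due in the break. A completed pair with both ratings in term but on opposite sides of the summer is expected in 0-18%, and in 0-2% at a 9-week interval.

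**Cost of restriction.** Children with both wears in term: 54-69%, about 16-21 of 30. Teacher pairs with no overlap with the summer: 43-67%, about 13-20 of 30. The 95% confidence interval half-width for a mean paired change, in SDs of the change, is 1.96/√n by normal approximation: 0.36 at n = 30, 0.44 at n = 20, 0.51 at n = 15 and 0.54 at n = 13.

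**The case against.** Several points on the other side have force.

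- **The analysis of teacher ratings is not written down.** The before-after sentence in Section 11.0 stands under the exploratory activity aim and names neither the Vanderbilt nor the IRS. A reader might infer that the plan commits to paired tests of teacher scores; it does not say so. This stands. However, no other analysis is offered for outcomes measured at baseline and 9 weeks, and the activity comparison is explicitly within child.
- **Change of teacher is not shown to be common.** A reader might take the 33-57% overlap with the break as the share of pairs rated by two teachers. It is not: most overlapping pairs have a rating due inside the break, which is mainly a missing-data problem. The wording on reimbursement also reads most naturally as one teacher completing both batteries, though it is not a rule. The teacher consent forms mentioned in Section 30.0 are not available here.
- **Teachers are not the only raters outside the family.** The CGI-S is clinician-rated, appears in Table 2 at screening and 9 weeks, and is called an exploratory outcome in Section 3.4.
- **The timing inputs are soft.** The 9-16 weeks describes total participation, and Table 2 separates screening from baseline, so the gap between batteries may be nearer 9 weeks. Break length and even starts are assumed. With 4-5 groups the affected share moves in steps of several children.
- **The stakes are limited.** Section 11.0 makes feasibility and acceptability the main outcome and calls the analyses descriptive. The size and direction of any term-break difference in activity are not given.

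These points limit the size and importance of the concern. None of them supplies a rule for the school calendar.

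**Conclusion.** The concern holds as a modest improvement to an exploratory analysis. Followed as written, the plan mixes term and break wears in an uncontrolled estimate of MVPA change and gives the reader no way to see it. Under evenly spread starts and an 8-12 week summer break, about 31-46% of children would have exactly one wear in the break, and 31-46% would have at least one teacher battery due then. These are expectations under assumptions; the realised share in 4-5 groups could be well below or above them.

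The narrower claim, that a new teacher's rating is taken for change in the child, applies to about 0-18% of pairs, and to 0-2% at a 9-week interval. It also depends on the inferred before-after analysis of teacher scores. The main feasibility and acceptability aim is touched only where calendar-driven missing teacher batteries are counted as poor adherence.

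**What to change.** 1. Record teacher identity at each teacher battery, and whether school was in session at each teacher battery and each accelerometer wear.
2. In Section 11.0, report MVPA change for all children and, beside it, for children whose two wears were both in school weeks.
3. State how teacher ratings are analysed: change in same-teacher, in-term pairs shown beside all available pairs, with a sentence on how missing teacher ratings are handled.
4. Report the number of evaluable teacher pairs as a feasibility result, so that ratings lost to the calendar can be told apart from poor adherence.
5. Keep rolling starts. Tying groups to the school year is not needed for this.

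The cost is two extra data fields and less precision in the restricted sets. Because the full-sample estimates are kept, no child's data are discarded. The fields are easy to collect at the time and hard to reconstruct later.
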